9.1. Study population

HIV-infected and uninfected pregnant women aged 18-40 years who will be attending Antenatal care at Kawempe National Referral Hospital, Kawaala or Komamboga Health Centre III or Wakiso or Kisenyi Health Centre IV, Uganda and who meet the inclusion criteria.

Kawempe national referral hospital is a national referral hospital, while Kawaala and Komamboga Health Centre III and Wakiso and Kisenyi health centre IV are health centres under the Kampala Capital City Authority.

All hospitals have fully equipped emergency area including resuscitation and operation rooms. Both hospitals have fully equipped antenatal, labour and delivery, post-natal and EPI services.

9.2. Data collection

Data will be collected regarding: previous vaccinations (mother), parity, gravida, illnesses or complications of pregnancy, gestation at birth, birth weight, HIV status (mother and infant), syphilis and hepatitis B and hepatitis C status, CBC, renal and liver function, CD4 count, HIV viral load, medications, maternal age, ethnicity, infant sex and number of siblings. All patient information will be directly inputted into the database using only the unique study identifier.

9.3. Patient randomisation

Participants will be randomized to either receive one dose of GBS6 vaccine or Placebo as a single injection on Day 1.

Stratified Block randomization will be used in this study. Randomization will be done in blocks of eight (8) in an automated system of Stata, stratified by HIV status and the list uploaded in the REDCap database. Participants will be randomized onto either arm (trial vaccine or placebo) of the study at enrolment by the data manager. The groups within REDCap will be labelled (A and B) and only the data manager will have access to the randomization

A placebo controlled clinical trial investigating the safety and immunogenicity of GBS6 in pregnant women with and without human immunodeficiency virus (HIV) infection and their infants

Protocol Version 5.0, Dated 01/02/2023

Protocol Version/date 5.0,01/02/2023
R&D Protocol Code Number:
Page:49

MAKERERE UNIVERSITY
SCHOOL OF MEDICINE
APPROVED AMENDMENT
Valid Until

★ 30 NOV 2023 ★

RESEARCH & ETHICS COMMITTEE
[name]

CRF, but the data manager will not be aware of which group (A or B) is the trial vaccine or placebo. Equal numbers will be allocated into each group (total n=300, 75 per group), with randomisation stratified by HIV status.

During the screening visit, the Data Manager will enter the participant's Screening ID into the REDCap system and complete the Randomization eCRF to randomise a participant. Once the participant is randomised, the REDCap system will randomly allocate the participant to either arm A or B as above. This will be notified automatically to the unblinded pharmacist. The unblinded pharmacist will take the notification and prepare the vaccine/placebo accordingly. The participants will use the same randomisation number throughout the study. The pharmacist will retain the lists of the allocation of unblinded medication prepared. The list must be kept in a safe place away from the blinded study team and will be monitored by the unblinded monitor.

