11.1. Maternal participants

11.1.1 Visit 0- Screening

Participants will be screened from 2 to 14 days prior to administration of the investigational product to confirm that they meet eligibility (all of the inclusion and none of the exclusion) criteria for the study.

If the participant is found ineligible for the study on the basis of screening laboratory assessment and repeat testing is not warranted, the investigator may advise the participant of the results by telephone, and the participant will be withdrawn from further participation in the study. All eligible participants will proceed to Visit 1.

The following procedures will be performed:

- Obtain written informed consent before performing any study-specific procedures.
- Assign a single participant identifier using the RedCAP system.
- Obtain and record the participant demographic data (including date of birth, sex, race, and ethnicity). The complete date of birth (dd-mmm-yyyy) will be collected to critically evaluate the immune response and safety profile by age.
- Obtain and record current alcohol and tobacco usage.
- Obtain and record any medical and obstetric history of clinical significance including history from prior and current pregnancy(ies).
- Obtain and record any immunisation history during pregnancy such as tetanus containing vaccines (TT and Td) or influenza vaccines vaccination from prior and current pregnancy(ies).
- Record the last normal menstrual period (LMP) and estimated date of delivery (EDD).
- Measure vital signs, including weight, height, oral temperature, sitting blood pressure and pulse rate, and respiratory rate.

A placebo controlled clinical trial investigating the safety and immunogenicity of GBS6 in pregnant women with and without human immunodeficiency virus (HIV) infection and their infants

Protocol Version 5.0, Dated 01/02/2023

Protocol Version/date 5.0,01/02/2023
R&D Protocol Code Number:
Page:60

MAKERERE UNIVERSITY
SCHOOL OF MEDICINE
APPROVED AMENDMENT
Valid Until

★ 30 NOV 2023 ★

RESEARCH & ETHICS COMMITTEE
[name]

- Perform physical examination evaluating any clinically significant abnormalities within the following body systems: general appearance; skin; head, eyes, ears, nose, and throat; heart; lungs; abdomen; musculoskeletal; extremities; neurological; and lymph nodes. Abnormal results must be recorded on source documents and the physical examination page of the CRF.

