- Perform obstetric examination including but not limited to scars from previous deliveries, fundal height, foetal heart tones, and foetal movement.
- Perform obstetric ultrasound and record findings.
- Ensure and document that all of the inclusion criteria and none of the exclusion criteria are met (see Section 8).
- Obtain blood sample (approximately 2 x 5 mL) for HBV, HCV, HIV, syphilis testing , CBC, renal and liver function. Participants newly testing positive for HIV, acute or chronic HBV, HCV, or syphilis will not be eligible for randomisation.
- Obtain urine sample for glucose and protein testing (urine dipstick).
- Complete the source documents.
- Record non-study vaccinations and medications (including antibiotic medications) as described in Section 10.9.
- The investigator or an authorised designee completes the CRF.

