30 NOV 2023

RESEARCH & ETHICS COMMITTEE
[name]

Schedule of Activities for Maternal Participants											
Visit Number	0	1	2	3	4	5	6	7	8	9	
Visit Description	Screening	Vaccination	2-Week Follow-up	1-Month Follow-up	Delivery	1-Week Postdeliv. v.	6-Week Postdeliv. Follow-up	18-Week Postdeliv. Follow-up	6-Month Postdeliv. Follow-up	12-Month Postdeliv. Follow-up	
Visit Window (Days)	Day -14 to Day -2 Prior to Day 1	Day 1	14-17 Days After Visit 1	28-42 Days After Visit 1	Varies	7-10 Days After Visit 4	35-49 Days After Visit 4	120-140 Days After Visit 4	160-200 Days After Visit 4	365-385 Days After Visit 4	
Type of Visit	Clinic	Clinic	Clinic	Clinic	Hospital	Phone Call	Clinic	Clinic	Phone Call	Clinic	
Review temporary delay criteria		X									
Review continued eligibility		X	X	X	X	X	X	X	X	X	
Record systemic events at baseline in the paper diary card		X									
Assign single participant identifier	X										
Assign participant randomisation and container number		X									

A placebo controlled clinical trial investigating the safety and immunogenicity of GBS6 in pregnant women with and without human immunodeficiency virus (HIV) infection and their infants

Protocol Version 5.0, Dated 01/02/2023

Protocol Version/date 5.0,01/02/2023

R&D Protocol Code Number:

Page:77

MAKERERE UNIVERSITY
SCHOOL OF MEDICINE
APPROVED AMENDMENT
Valid Until

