15.2. Recruitment

Women will be recruited after 20 weeks gestation at antenatal clinic at Kawempe National Referral Hospital, Kawaala or Komamboga Health Centre III, Wakiso or Kisenyi Health Centre IV, following an ultrasound dating scan confirming a low risk, singleton pregnancy and a confirmatory HIV test. Women will be randomised to receive either a placebo or GBS6 vaccination after recruitment.

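### Section 9.3 places randomisation at the screening visit, against 11.1.1 and Table 1, so women whose eligibility results are pending would be randomised and some never dosed

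*Protocol*

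**What the plan says.** Protocol section 9.3 gives two timings. It first states "Participants will be randomized onto either arm (trial vaccine or placebo) of the study at enrolment by the data manager". It then gives the operating instruction: "During the screening visit, the Data Manager will enter the participant's Screening ID into the REDCap system". At that same visit the data manager is also to "complete the Randomization eCRF to randomise a participant". This is allocation and not mere registration, because REDCap then assigns arm A or B and automatically notifies the unblinded pharmacist.

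Other parts of the protocol place the act later or make it depend on results:

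- Section 11.1.1 (Screening): "Participants will be screened from 2 to 14 days prior to administration of the investigational product". The HIV, HBV, HCV, syphilis, blood count, renal and liver samples are drawn at this visit, and "Participants newly testing positive for HIV, acute or chronic HBV, HCV, or syphilis will not be eligible for randomisation". For a woman who fails on laboratory grounds, "the investigator may advise the participant of the results by telephone, and the participant will be withdrawn from further participation in the study". Only eligible women go on to Visit 1.
- Section 11.1.2 (Visit 1): laboratory results, continued eligibility and the temporary-delay criteria are reviewed before dosing.
- Table 1 (maternal schedule): the row "Assign participant randomisation and container number" is marked at Visit 1 only. The row for the participant identifier is marked at Visit 0, so the schedule treats these as separate acts.
- Section 15.2: "Women will be randomised to receive either a placebo or GBS6 vaccination after recruitment".

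Neither of the procedure lists in 11.1.1 and 11.1.2 contains a randomisation step, so they do not settle the matter.

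**The concern.** A data manager who follows 9.3 allocates a woman on the day her screening blood is drawn. Section 11.1.1 cannot then be obeyed, because the results that decide whether she may be randomised come later. Any woman lost between that visit and the dose is randomised but undosed. She uses a position in a block of eight and counts among those assigned in the CONSORT flowchart described in 6.3.

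Decisions that involve judgement would also follow allocation: whether an abnormal result is repeated (Table 1, note c), whether vaccination is postponed (8.5), and whether the woman remains eligible. Good practice is to close these decisions before the allocation exists.

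**Working it through.** **Timing, side by side**

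| Source in protocol | When randomisation happens |
|---|---|
| 9.3, first statement | Enrolment |
| 9.3, operating instruction | Screening visit, 2 to 14 days before dosing |
| 11.1.1 | Only once new positives have been ruled out |
| Table 1 | Visit 1 |
| 15.2 | After recruitment (no visit named) |

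Could the results be available on the screening day? Sections 15.3 and 15.4 mention point-of-care screening for syphilis, hepatitis B and HIV, so those might be. Section 12.1 sends the screening tests to an outside laboratory. HCV, blood count, renal and liver results are all needed for inclusion criteria 4 and 5, and nowhere are they described as same-day. At least those would be pending.

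**The plan's own power figures (section 6.1)**

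- Prematurity, 10% v 22%, 150 per arm, two-sided 5%: Φ[(0.12·√150 − 1.96·√(2·0.16·0.84)) / √(0.10·0.90 + 0.22·0.78)] = Φ(0.887) = 81.2%.
- Antibody, 3.24-fold, SD 2.55 log e, 75 per group: standard error 2.55·√(2/75) = 0.416; ln 3.24 = 1.176; Φ(1.176/0.416 − 1.96) = 80.6%.

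Both agree with the stated 80%. They are not in dispute.

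**Effect of losses between randomisation and dosing**

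The protocol gives no such rate, so d below is an assumption.

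- Number to randomise = 300/(1 − d), rounded up.
- Imbalance comes from simulation: 10,000 runs per rate, blocks of eight, each randomised woman lost independently with probability d, continuing until 150 in a stratum are dosed.
- The power columns assume no replacement, with 150(1 − d) per arm for prematurity and 75(1 − d) per group for antibody.

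| d | Randomised to dose 300 | Never dosed | Mean difference between arms within a stratum | Prematurity power, no replacement | Antibody power, no replacement |
|---|---|---|---|---|---|
| 0 | 300 | 0 | 0.9 | 81.2% | 80.6% |
| 5% | 316 | 16 | 2.3 | 79.2% | 78.6% |
| 10% | 334 | 34 | 3.2 | 77.0% | 76.4% |
| 20% | 375 | 75 | 4.3 | 72.0% | 71.4% |
| 30% | 429 | 129 | 5.4 | 66.2% | 65.6% |

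The 0.9 with no loss arises because 150 is not a multiple of 8.

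**With replacement**

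Section 10.11 allows replacement before vaccination, and then only the imbalance matters. Even a split of 65 v 85 gives Φ(1.176/(2.55·√(1/65 + 1/85)) − 1.96) = 79.9%. That difference of 20 exceeds the 95th percentile of 14 simulated at 30% loss.

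**The case against.** The strongest reply is that this is one misplaced phrase. Table 1, 11.1.1, 11.1.2 and the first statement in 9.3 all fit randomisation on the dosing day, and so does having the pharmacist prepare the product on receiving the notice. The consequences are also limited. The safety population is dosed women (6.2). The mITT population needs an assay result, and the first immunogenicity sample is taken at Visit 1, so women lost before it fall outside both. The flowchart separates those assigned from those vaccinated. This stands, and it limits the size of the problem. It does not remove the contradiction, since the phrase sits in the instruction that the data manager will follow.

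Three stronger readings are tempting and are not supported:

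- **Women analysed in the wrong HIV stratum.** Inclusion criteria 6 and 7 require a documented HIV test in pregnancy and, for women with HIV, at least two months on antiretroviral therapy. Section 15.2 places recruitment after an HIV test. The stratum is therefore normally known. A woman newly positive at screening is ineligible, so she is a loss and not a misclassified participant.
- **A known, large number of undosed women.** Age, BMI, obstetric history, ultrasound and examination can be checked at the screening visit before the form is completed. Only later failures count, and the protocol gives no rate for them.
- **Bias or leakage.** Laboratory failures on blood drawn before dosing cannot be caused by the allocation. The data manager sees only A or B, and the pharmacist's list is kept from the blinded team. The longer interval is untidy, but nothing in the protocol shows a leak.

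**Conclusion.** The point holds as an internal contradiction about trial conduct. Section 9.3 disagrees with itself, with 11.1.1 and with Table 1, and its operating instruction is the version that randomises women before laboratory eligibility is known. The cost is real but modest: wasted block positions, a few women of imbalance per stratum, a larger randomised count, and discretionary eligibility decisions made after allocation.

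The number of women affected cannot be computed from the protocol. The range of 316 to 429 randomised to dose 300 rests wholly on an assumed 5% to 30% loss after screening. The small effect on power assumes that losses are replaced, which 10.11 permits but does not require. Without replacement, power would fall as in the table. The absence of bias assumes that blinding holds. The stated power figures stand, and no analysis in the wrong stratum is expected.

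**What to change.** In 9.3, delete the reference to the screening visit. State that the data manager completes the randomisation form at Visit 1, after screening results, continued eligibility and temporary-delay criteria have been reviewed and immediately before dispensing, as Table 1 shows. Make the enrolment statement in 9.3 and the sentence in 15.2 point to the same moment, and add a randomisation line to the Visit 1 list in 11.1.2. The identifier can still be assigned at screening.

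The cost is a wording amendment. Sample size, analyses and visit schedule do not change. The pharmacist would prepare the dose on the day of the notice, which is what Table 1 already implies.

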9.4. Blinding of the Site Personnel

This is a double blinded study. Study nursing staff and participants will be blinded to the vaccine given and vaccine syringes will be covered with an opaque label, obscuring the vaccine. Only the preparing pharmacist(s) (unblinded dispenser(s)) will be aware of the vaccine used. The vaccine will be administered by a trained nurse who will only give the vaccine and have no other participation in the study. A study nurse who is blinded to the vaccine given will observe for immediate reactions to the vaccine in a separate room from where the woman will receive her vaccination. This room will have an emergency trolley with appropriate drugs available should these be required. At least one unblinded dispenser and a backup will be assigned. A member of the study site staff not responsible for monitoring safety in the study or clinic pharmacy should fulfill this role. Contact between the unblinded dispenser(s) and study participants should be kept to a minimum. The investigator, study coordinator, and any site staff other than the unblinded dispenser(s)

A placebo controlled clinical trial investigating the safety and immunogenicity of GBS6 in pregnant women with and without human immunodeficiency virus (HIV) infection and their infants

Protocol Version 5.0, Dated 01/02/2023

Protocol Version/date 5.0,01/02/2023
R&D Protocol Code Number:
Page:50

MAKERERE UNIVERSITY
SCHOOL OF MEDICINE
APPROVED AMENDMENT
Valid Until

30 NOV 2023

RESEARCH & ETHICS COMMITTEE
[name]

must not be allowed to know the investigational product assigned to any study participant and must not be allowed to see the investigational product containers. The laboratory-based research team conducting the assays will be blinded to subject allocation.

9.5. Blinding of the Sponsor

In this study, the sponsor study team members will remain blinded to vaccine assignment of all participants enrolled. Laboratory personnel performing the serological assays will remain blinded to vaccine assigned/received throughout the study.

9.6. Schedule of activities (refer to Table 1 and 2)

Maternal participant

Screening: 2x5mls blood drawn for HBV, HCV, HIV and syphilis, CBC, renal and liver function testing. ICF, review medical history, dating ultrasound and review eligibility criteria. Review pregnancy immunisation history to endure participants have had two doses of tetanus vaccines at least 14 days prior to GBS6 immunisation. To test for glucose and protein, urine samples will be obtained.

Visit 1 (Day 1): Maternal participant will be administered GBS6 or placebo. 1x10mls blood drawn for immunogenicity assessment. To determine GBS status, one rectal and one vaginal swab will be performed. 1x5mls blood drawn for CD4 and viral load testing. Women will be asked to keep a symptom diary for 7 days post vaccination.

Visit 2 (2-weeks follow-up visit): 1x10mls blood drawn for immunogenicity assessment.

Visit 3: (1-month follow-up visit): 1x10mls blood drawn for immunogenicity assessment.

Visit 4 (Delivery): 1x10mls blood drawn for immunogenicity assessment and one rectal and one vaginal swab to determine GBS status. 1x2mL of colostrum (within 72 hours of birth)

Visit 5 (1 week post delivery): telephone call to check on health

Visit 6 (6-weeks post-delivery): 1x10mls blood drawn for immunogenicity assessment and one rectal and one vaginal swab to determine GBS status. 1x5mL of breastmilk

Visit 7 (18 weeks post delivery): 1x5mL breastmilk, urine pregnancy test (dipstick)

A placebo controlled clinical trial investigating the safety and immunogenicity of GBS6 in pregnant women with and without human immunodeficiency virus (HIV) infection and their infants

Protocol Version 5.0, Dated 01/02/2023

Protocol Version/date 5.0,01/02/2023
R&D Protocol Code Number:
Page:51

Visit 8 (6 months post-delivery): telephone call to check on health and pregnancy.

Visit 9 (12-months post-delivery): 1x10mls blood drawn for immunogenicity assessment, urine pregnancy test (dipstick).

If any participant is found to be pregnant in any visit from Visit 7-9 then they will be asked for permission to follow this subsequent pregnancy and directed to antenatal care. No additional investigations or visits are planned in the event that a participant has a subsequent pregnancy but data collection will occur in addition to the original pregnancy to assess safety (see section 14.14.2. below).

Infant participant

Visit 4 (Delivery): 1x10mls cord blood drawn for immunogenicity assessment, dried blood spot card collection and nasal/rectal swab to determine GBS status.

Visit 5 (1 week post-delivery): telephone call to check on health

Visit 6 (6-weeks post-delivery): Infant ~5mls blood at 6 weeks and nasal/rectal swab to determine GBS status.

Visit 7 (18-weeks post-delivery): Infant ~5mls blood and nasal/rectal swab to determine GBS status.

Visit 8 (6 months post-delivery): telephone call to check on health

Visit 9 (12-months post-delivery): Infant ~5mls blood at 12 months.

A placebo controlled clinical trial investigating the safety and immunogenicity of GBS6 in pregnant women with and without human immunodeficiency virus (HIV) infection and their infants

Protocol Version 5.0, Dated 01/02/2023

Protocol Version/date 5.0,01/02/2023

R&D Protocol Code Number:

Page:52

10. Trial Investigational Product

All maternal participants will receive either a placebo or GBS6. This vaccine will be given at the time period assigned by randomisation. **No vaccine will be given as part of the study at ≤ 26 6/7 Gestational weeks as per inclusion/exclusion criteria.**

10.1. Investigational Product Supplies

GBS6 and placebo (saline control) will be provided by Pfizer.

Study vaccines will be packed and labeled as investigational product in accordance with current guidelines and applicable local and legal regulatory requirements. The formulation of the investigational products is described below.

10.2. Name and description of investigational medicinal product (IP)

The investigational products are GBS6 and placebo (saline control). The GBS6 will be 20mcg without AlPO4 (equivalent to 240 mcg/mL) /0.5mL dose or 20 mcg CPS/serotype)

Participants will receive 1 dose of GBS6,without AlPO₄, or placebo (saline control) at Visit 1 administered intramuscularly by injecting 0.5 mL into the deltoid muscle, preferably of the nondominant arm.

10.3. Preparation and Dispensing

Investigational product preparation and dosing information will be provided in the investigational product (IP) manual.

GBS6 and placebo will be prepared by qualified unblinded site personnel according to the IP manual. The investigational product will be administered by qualified unblinded site personnel who keep the participants blinded, because of the difference in investigational product appearance.

A placebo controlled clinical trial investigating the safety and immunogenicity of GBS6 in pregnant women with and without human immunodeficiency virus (HIV) infection and their infants

Protocol Version 5.0, Dated 01/02/2023

Protocol Version/date 5.0,01/02/2023
R&D Protocol Code Number:
Page:53

Please refer to the IP manual for instructions on how to prepare the investigational product for administration.

10.4. Allocation to Investigational Product

The unblinded pharmacist will take the notification generated by the REDCap system described above and prepare the vaccine/placebo accordingly. The participants will use the same randomisation number throughout the study. The pharmacist will retain the lists of the allocation of unblinded medication prepared. The list must be kept in a safe place away from the blinded study team and will be monitored by the unblinded monitor. The pharmacist will indicate the randomisation number on the blinded vaccine for the study team to inject. The filled syringes will be covered with opaque tape to ensure that the participant is blinded to the allocation.

The participants will be allocated to an investigational product group as described above. Infants (infant participants) of the maternal participants will be assigned a participant number at birth.

